#### 4.4 End of Study (EOS) Definition

A participant is considered to have completed the study if he/she has completed all phases of the study including the last scheduled procedure shown in the Schedule of Activities. Trial site will have the option of either contacting participants within 2 to 5 days after surgery (by phone) or scheduling participants for an office appointment, depending on their standard of care policies, to assess the occurrence or persistence of AEs, any medications taken, and for adequate treatment and follow up.

##### Primary completion

The primary completion is defined as the date of the last visit of the last participant for the primary outcome.

### 5. Study Population

Prospective approval of protocol deviations to recruitment and enrollment criteria, also known as protocol waivers or exemptions, is not permitted.

The participant population will consist of healthy individuals who are status post extraction of three or four third molars, two of which were mandibular partial or full bony impactions.

#### 5.1 Inclusion Criteria

Participants are eligible to be included in the study only if all of the following criteria apply:

1. Healthy, ambulatory, male or female volunteers 16 years of age or older;
2. Body mass index 18.5 to 35.0 kg/m^2 inclusive as measured by the NIH BMI Calculator;
3. Participants will undergo surgical extraction of three or four third molars, two of which must be mandibular molars. Maxillary third molars may be removed regardless of impaction level. The mandibular extractions must have a trauma rating of mild or moderate and meet one of the following scenarios:
  - two full bony impactions
  - two partial bony impactions
  - one full bony impaction in combination with one partial bony impaction

Supernumerary teeth present may also be removed at the discretion of the oral surgeon;

5. Have not taken any form of medication, nutritional supplements with analgesic properties (e.g. GABA, turmeric) or herbal supplements (i.e., St. John's Wort) within 5 days of admission (except for oral contraceptives, prophylactic antibiotics, multivitamin supplements, or other routine medications to treat benign conditions (such as antibiotics to treat acne), and agree not to take any medication (other than that provided to them) throughout the study;

6. Female participants of childbearing potential must: a) be using a medically acceptable form of birth control [e.g., hormonal contraceptives (oral, patch, injectable or vaginal ring), implantable device (implantable rod or intrauterine device), or a double barrier] for at least 1 month prior to screening (3 months on oral contraceptives); b) abstain from sexual intercourse for at least 1 month prior to screening; or c) participate exclusively in a same sex relationship for at least 1 month prior to screening. In addition, female participants of childbearing potential must have a negative pregnancy test at Screening and prior to study drug administration. Female participants of non-childbearing potential must be amenorrheic for at least two years or have undergone surgical sterilization (i.e. tubal ligation/occlusion, hysterectomy and/or bilateral oophorectomy);
7. Have not consumed alcoholic beverages, or foods and beverages containing caffeine (examples; coffee, tea, chocolate, and colas) for 24 hours and for 2 days prior to surgery, respectively and agree not to consume any of these foods or beverages throughout their stay at the study site;
8. Use of only short-acting local anesthetic (e.g., mepivacaine or lidocaine) preoperatively, with or without a vasoconstrictor and nitrous oxide at the discretion of the Investigator;
9. Have moderate to severe postoperative pain on the Categorical Pain Intensity Scale (a score of at least 2 on a 4 point scale) and a score of  $\geq 5$  on the 0-10 pain intensity NRS within 4.5 hours post-surgery;
10. Ability to understand and follow study-related instructions;
11. Be willing and able to participate in all scheduled visits, treatment plan, and trial procedures according to the clinical protocol;
12. Capable of giving signed informed consent as described in Section 10.1.4 which includes compliance with the requirements and restrictions listed in the informed consent form (ICF) and in this protocol.

## 5.2 Exclusion Criteria

Participants are excluded from the study if any of the following criteria apply:

1. History of hypersensitivity to naproxen sodium, caffeine, ibuprofen, NSAIDS, aspirin, similar pharmacological agents, local anesthetics, rescue medication or components of the investigational products;
2. Evidence or history of clinically significant (in the judgment of the investigator) hematological, renal, endocrine, pulmonary, gastrointestinal, cardiovascular (including hypertension and cardiac arrhythmia), hepatic, psychiatric, neurologic diseases, or malignancies within the last 5 years;
3. Participants with the following medical conditions may be eligible at the discretion of the investigator: ADHD on a stable dose regimen of methylphenidate/(dextro) amphetamine for at least 6 months; participants with hypothyroidism on a stable dose of synthetic thyroid hormone for at least 6 months;
4. Have received any form of treatment in the form of medication for depression in the past 6 months or any form of psychotropic agent (including selective serotonin uptake

- inhibitors [SSRI] but excluding ADHD medications described above) within the last 6 months;
5. Relevant concomitant disease such as asthma (exercise induced asthma is permitted);
  6. Current or past history of gastrointestinal ulceration, gastrointestinal bleeding or other bleeding disorder(s);
  7. Acute illness or active local infection prior to surgery that can interfere with the conduct of the study in the judgment of the investigator;
  8. Use of any OTC or prescription medications with which the administration of naproxen, acetaminophen, ibuprofen, any other NSAID, (e.g., tramadol) or if a medication is contraindicated;
  9. Use of any medications within 5 days of surgery until discharge from the study site (except oral contraceptives, prophylactic antibiotics, synthetic thyroid hormones, methylphenidate or medications to treat benign conditions such as antibiotics to treat acne);
  10. Use of caffeine within 2 days prior to the study
  11. Habits of high consumption of caffeine (>400 mg/day equivalent to about 3-4 cups of coffee per day)
  12. Females who are planning to become pregnant, are pregnant or lactating;
  13. Habituation to analgesic drugs including opioids (i.e., routine use of oral analgesics 5 or more times per week for greater than 3 weeks within the past 2 years);
  14. Alcoholism or drug abuse within 2 years prior to the Screening Visit or routine consumption of 3 or more alcohol containing beverages per day; Alcohol containing beverages are defined as one beer (5%), one glass of wine (11%) and one shot (40%) hard liquor;
  15. Positive urine drug screen or alcohol test on day of surgery;
  16. Surgeon's trauma rating of severe following surgery;
  17. Use of Nicotine containing products from midnight prior to surgery until discharge from the study site or longer if so directed by the oral surgeon;
  18. Member or first-degree relative of study staff or the Sponsor directly involved in the study;
  19. Unwilling or unable to comply with all requirements outlined in the protocol;
  20. Participants with a medical disorder, condition, or history of such that could impair the participant's ability to participate or complete this trial in the opinion of the investigator;
  21. Previous enrollment in this study.

### **5.3 Lifestyle Considerations**

No lifestyle restrictions are required.

### **5.3.1 Meals and Dietary Restrictions**

Participants will be instructed not to consume food that contains caffeine (e.g., chocolate, ice cream) two days prior to surgery.

### **5.3.2 Alcohol**

Participants will be instructed not to consume alcohol beverages 24 hours prior to surgery.

## **5.4 Screen Failures**

Screen failures are defined as participants who consent to participate in the clinical study but are not subsequently randomly assigned to study intervention. A minimal set of screen failure information is required to ensure transparent reporting of screen failure to respond to queries from regulatory authorities. Minimal information includes demography, screen failure details, eligibility criteria, and any serious adverse event (SAE).

Individuals who do not meet the criteria for participation in this study (screen failure) due to scheduling surgery may be rescreened. A previous dental x-ray if taken during the original screening visit can be used when rescreened. Rescreened participants should be assigned a new participant number.

## **5.5 Run-in Failures**

A participant who, for any reason terminates the study after surgery and prior to the start of study drug administration (e.g., not meeting pain threshold) is regarded as a “Run-in failure”.

## **5.6 Dropouts**

A participant who discontinues study participation prematurely for any reason is defined as a “dropout” if the participant has been randomized and administered at least one dose of study drug.

## **5.7 General Procedures**

In all cases, the reason for withdrawal must be recorded on the screening log and in the participant's medical records.

The participant may object to the generation and processing of post-withdrawal data as specified in Section 10.1.8.

Details for the premature termination of the study as a whole (or components thereof) are provided in Section 10.1.14 (Premature termination of the Study).

## 6. Study Intervention

Study intervention is defined as any investigational intervention(s), marketed product(s), placebo, or medical device(s) intended to be administered to a study participant according to the study protocol.

The study center will dispense a single-dose CCI of an assigned treatment within 4.5 hours post-surgery. The tablets and placebo will be administered based on a computer-generated randomization schedule (section 6.1.1) and the severity of pain experienced (moderate or severe). Participants who characterize their pain severity as mild and have a NRS <5 will not receive treatment and will be discharged from the study site with a prescription for pain medication, if deemed safe, by an Investigator.

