### 6.1.1 Study intervention assignment

At the beginning of the first treatment period, after completion of the pre-treatment baseline procedures/assessments, participants who meet the entry criteria will be sequentially assigned to a unique number in sequential order (randomization number, RNR) according to the randomization schedule 2:2:2:2:2:1:1 (naproxen sodium/caffeine [CCI], naproxen sodium/caffeine [CCI]; naproxen sodium [CCI], naproxen sodium/caffeine [CCI], naproxen sodium [CCI]; caffeine [CCI]; placebo) prepared prior to the study.

Participants will be numbered according to the following scheme:

[PPD]

Whereas the “Xs” will be replaced with a four digit sequentially assigned number as each participant enters the study (e.g., first participant number will be [PPD]).

The unique participant identifier number will be assigned in numerical order prior to dosing. Participants who characterize their pain severity as *mild* and <5 on the NRS will not receive treatment and be withdrawn from the study.

Once a number has been assigned to a participant, it cannot be reassigned to another participant.

Participants completing the Screening Visit, if not scheduled for surgery the same day, will return to the trial site within 28 days, and if they continue to meet inclusion/exclusion criteria post-surgery will be randomized to one of seven treatment groups:

- naproxen sodium/caffeine [CCI]
- naproxen sodium/caffeine [CCI]
- naproxen sodium/caffeine [CCI]
- naproxen sodium/caffeine [CCI]
- naproxen sodium [CCI]
- caffeine [CCI]
- placebo (2 tablets)

Participants will be assigned to treatment groups in accordance with the randomization schedule. The Sponsor will provide a randomization schedule to the study site.

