## 6.2 Preparation/Handling/Storage/Accountability

All study drugs will be labeled according to the requirements of local law and legislation. Label text will be approved according to the sponsor's agreed procedures, and a copy of the labels will be made available to the study site upon request.

For all study drugs, a system of numbering in accordance with all requirements of Good Manufacturing Practice (GMP) will be used, ensuring that each dose of study drug can be traced back to the respective bulk batch of the ingredients. Lists linking all numbering levels will be maintained by the sponsor's clinical supplies Quality Assurance (QA) group.

A complete record of batch numbers and expiry dates of all investigational products as well as the labels will be maintained in the clinical supply file.

The source of test and reference products will be documented in the clinical supply file.

The investigator or designee must confirm appropriate temperature conditions have been maintained during transit for all study intervention received and any discrepancies are reported and resolved before use of the study intervention. Only participants enrolled in the study may receive study intervention and only authorized site staff may supply or administer study intervention. All study intervention must be stored in a secure, environmentally controlled, and monitored (manual or automated) area in accordance with the labeled storage conditions with access limited to the investigator and authorized site staff. The investigator, institution, or the head of the medical institution (where applicable) is responsible for study intervention accountability, reconciliation, and record maintenance (i.e., receipt, reconciliation, and final disposition records).

The Sponsor will provide sufficient quantity of the IMP to the study site. The study center will dispense IMP according to the randomization schedule and the participant's categorical pain intensity (moderate or severe) post-surgery. IMP will be supplied to the study center in multi-dose bottles and dispensed by an unblinded member of the study team.

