## 7.2 Participant Discontinuation/Withdrawal from the Study

### Withdrawal criteria

Participants *must* be withdrawn from the study if any of the following occurs:

- A participant may withdraw from the study at any time at his/her own request, or may be withdrawn at any time at the discretion of the investigator for safety, behavioral, compliance, or administrative reasons. This is expected to be uncommon.
- At the time of discontinuing from the study, if possible, an early discontinuation visit should be conducted, as shown in the SoA. See SoA for data to be collected at the time of study discontinuation and follow-up and for any further evaluations that need to be completed.
- The participant will be permanently discontinued both from the study intervention and from the study at that time.
- If the participant withdraws consent for disclosure of future information, the sponsor may retain and continue to use any data collected before such a withdrawal of consent.
- Participant's pain intensity post-surgery at pre-dose does not exceed 'mild' and the NRS is <5 (see Section 10.5);
- If, in the Investigator's opinion, continuation of the study would be harmful to the participant's well-being;

Participants *may* be withdrawn from the study if any of the following occurs:

- Participant experiences one or more serious adverse events;
- At the specific request of the Sponsor and in consultation with the Investigator (e.g., obvious non-compliance, safety concerns);
- Protocol violation: if the participant develops conditions, which would have prevented his/her entry into the study according to the inclusion/exclusion criteria, he/she must be withdrawn immediately if safety is concerned; in other cases, the investigator will decide whether there is a conflict with the study objectives.

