#### 8.1.6 Postsurgery

During the post-surgery recovery period, participants will rest quietly, but will be encouraged not to fall asleep. Participants will be permitted to drink clear liquids following surgery. Participant may incorporate foods according to a soft diet following dosing beginning 60 minutes after dosing. Participants will not be allowed to eat 30 minutes prior to any planned assessments.

In order to qualify for randomization and continue in the trial, participants must have 'moderate' or 'severe' postoperative pain intensity on the Categorical Pain Rating Scale **and** a score of  $\geq 5$  on the NRS within 4.5 hours of the last suture.

Eligible participants will be assigned a participant randomization number and investigational products will be administered according to a generated randomization schedule (see Section 6.1.1).

Participants who have not met the randomization criteria within 4.5 hours from last suture or 14:30 h will not be randomized and may be discharged from the clinic, once deemed eligible by an Investigator. Prior to being released from the clinic, discharge procedures will be reviewed with the participant. When discharged, all participants will need to make prior arrangements for travel and should not drive themselves home.

After the baseline (pre-dose) pain intensity is determined, pain intensity and pain relief will be rated by participants at 0.5, 1, 1.5, 2, 3, 4, 5, 6, 7, 8, 9, 10, 11, and 12 hours (+/-5 minutes over the first 6 hours; +/-5 minutes from hours 7 through 12) post-dose, and immediately prior to the use of the first dose rescue medication.

CCI

CCI [REDACTED]

CCI [REDACTED]

CCI [REDACTED]

This answer will be recorded by the study coordinator in the case report form. CCI [REDACTED]

CCI [REDACTED]

CCI [REDACTED]

CCI [REDACTED]

Participants will stay awake during the entire 12 hour assessment. The order of the pain assessments is Pain Intensity, then Pain Relief, then query about any AEs. At hour 12 or immediately prior to the first dose of rescue medication (if prior to hour 12), study participants will be asked to provide a Global Assessment of investigational product after completion of the other assessments. Additionally, participants will have vital signs taken after surgery then at 1 and 12 hours post-dose.

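### Do participants whose two pain scores disagree slip past the dosing rules?

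*Protocol*

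**What the plan says.** **Entry.** Protocol section 5.1 opens with "Participants are eligible to be included in the study only if all of the following criteria apply". Criterion 9 joins two conditions by *and*: a categorical score of at least moderate, and an NRS of 5 or more, within 4.5 hours of surgery. Section 8.1.6 repeats the gate: "In order to qualify for randomization and continue in the trial, participants must have 'moderate' or 'severe' postoperative pain intensity", again together with an NRS of 5 or more. The same section says that anyone who has not met these criteria by the time limit is not randomised. The first paragraph of section 6.1.1 gives a randomisation number only to people who meet the entry criteria. Section 5 rules out waivers.

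**Non-treatment and withdrawal.** Three sentences use a narrower description:

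- Section 6: "Participants who characterize their pain severity as mild and have a NRS <5 will not receive treatment".
- Section 6.1.1: those with mild pain "and <5 on the NRS will not receive treatment and be withdrawn from the study".
- Section 7.2, mandatory withdrawal: "pain intensity post-surgery at pre-dose does not exceed 'mild' and the NRS is <5".

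**Dispensing.** Section 6.2 has the product dispensed by the randomisation schedule and by the participant's "categorical pain intensity (moderate or severe) post-surgery". The NRS is not mentioned there.

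**The concern.** The opposite of *both conditions met* is *at least one failed*. Sections 6, 6.1.1 and 7.2 instead describe *both failed*. A participant with moderate pain and an NRS of 3 or 4, or with mild pain and an NRS of 5 or more, fails entry but is named by none of the three sentences. The first of these also has the categorical rating that section 6.2 asks for.

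If such people were dosed, there would be two costs. They would have violated an inclusion criterion and could be removed from the per-protocol population, which carries the primary analysis (section 9.3), in arms of only 15 to 30. If they were kept, those with a low baseline NRS would have less room to improve on SPID0-8.

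**Working it through.** The plan gives no figure on this point, so the check is one of logic. The inputs are the two scales in Protocol section 10.5 and the rules set out above.

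**Step 1. Count the score pairs.** The categorical scale has 4 levels (0 to 3) and the NRS has 11 (0 to 10), so there are 4 × 11 = 44 pairs. Entry needs a categorical score of 2 or 3 and an NRS of 5 to 10: 2 × 6 = 12 pairs. The other 44 − 12 = 32 are ineligible.

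**Step 2. See which ineligible pairs each rule names.**

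| Rule | Pairs named | Ineligible pairs not named |
|---|---|---|
| Sections 6 and 6.1.1: mild, NRS below 5 | 1 × 5 = 5 | 32 − 5 = 27 (11 no pain; 6 mild with NRS 5 or more; 10 moderate or severe with NRS below 5) |
| Section 7.2: none or mild, NRS below 5 | 2 × 5 = 10 | 32 − 10 = 22 (12 none or mild with NRS 5 or more; 10 moderate or severe with NRS below 5) |
| Section 8.1.6: randomisation criteria not met in time | 32 | 0 |

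No rule excludes an eligible pair. The narrow rules are incomplete, but they do not collide with the entry gate.

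**Step 3. Ask whether any rule admits an unnamed pair.** The sentences in sections 6, 6.1.1 and 7.2 state who is *not* treated or is withdrawn; they do not say that everyone else is treated. Taken as a full list, the wording in sections 6 and 6.1.1 would also leave open the dosing of someone with no pain at all (11 of the 27 pairs). Nobody would read it that way, which shows that these are partial restatements.

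The categorical condition in section 6.2 covers 2 × 11 = 22 pairs, 10 of them ineligible. But the schedule is the other condition in the same sentence, and section 6.3 ties each dose to a randomisation number. Someone who was never randomised has no entry on the schedule. Section 5.5 already has a name for such a person: a run-in failure, for which it gives a missed pain threshold as the example.

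**Step 4. Check the feared size.**

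- *Losses.* Section 9.2 plans 180 evaluable: 5 × 30 + 2 × 15 = 180. With 5% drop-out, 180 / 0.95 = 189.5, rounded up to 190, an allowance of 10. If 2% to 10% of 190 had discordant scores, that would be 3.8 to 19 people. The 2% to 10% is an assumption with no basis in the documents. The count also needs the site to dose each of them against sections 5.1, 6.1.1 and 8.1.6.
- *Ceiling.* The 0–8 hour intervals sum to 4 × 0.5 + 6 × 1 = 8, so SPID0-8 cannot exceed 8 × baseline NRS: 24 at 3, 32 at 4, and 40 at 5. The ceiling is therefore 40% lower at 3 and 20% lower at 4 than at 5. It is not lower for mild pain with an NRS of 5 or more. Baseline pain intensity is also a covariate in the primary model (section 9.4.1; SAP section 6.1.4).

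**The case for a change.** The strongest case for a change concerns site conduct. Two places state the full gate, while four describe something narrower, each at a point where someone acts: treat, withdraw or dispense. Stating a consequence for one group invites the inference that others proceed. The person dispensing has no other study role (section 6.3), and the instruction in section 6.2 would not by itself reveal that an NRS below 5 had been missed upstream. The mandatory rule in section 7.2 would not require withdrawal of a discordant participant enrolled by mistake. Correcting this needs about four sentences, and both scores are already collected before dosing.

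The description of the wording stands, and misapplication is possible. But it would take a breach of the gate in sections 5.1, 6.1.1 and 8.1.6, which is a conduct error and not something the plan directs. Such an error has a place in the plan: deviations that lead to exclusion are identified and summarised, all deviations are supplied before database lock and listed (SAP section 6.3), significant eligibility violations may be treated as major, and the ITT population serves for sensitivity analysis (Protocol section 9.3). Because treatment is a single dose, a wider withdrawal rule could not undo an erroneous dosing either.

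**Conclusion.** The concern does not hold as a fault in the plan. Sections 6, 6.1.1 and 7.2 are not the logical opposite of the entry criterion, and section 6.2 omits the NRS. That is a clerical looseness. The gate itself is stated in full twice, and section 8.1.6 covers all 32 ineligible score pairs. A participant whose scores disagree may still qualify within the time window, and otherwise leaves before randomisation.

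Followed as written, the plan doses no one with discordant scores. Rewording would leave the randomised set, the analysis populations and the SPID0-8 comparison as they are. The range of 4 to 19 people rests on an assumed discordance rate and on assumed breaches of the gate, so it is not an estimate of harm.

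This conclusion assumes that site staff apply sections 5.1 and 8.1.6 before assigning a number, as section 6.1.1 requires. If the protocol is reopened for another reason, the passages can be reconciled to one criterion that the sponsor confirms. That would be editorial, and this review takes no position on what the criterion should be.
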